## 1. Abstract

*a.* Provide no more than a one page research abstract briefly stating the problem, the research hypothesis, and the importance of the research.

Primary progressive aphasia is a common type of neurodegenerative disease that affects first and foremost language abilities. Mild cognitive impairment is slowly progressive decline in a single domain of cognition (e.g. language) not attributable to motor or sensory loss, without impediment of social or occupational function (Petersen & others, 2003). MCI can be an early sign of neurodegenerative disease, or can be due to normal aging. When language is the prominent affected domain in MCI, the person may later meet criteria for PPA or may progress to the clinical syndrome of Alzheimer's dementia. Spelling, naming, and working memory (i.e. repetition) are among the language abilities affected early in the course of PPA, and different variants of Primary Progressive Aphasia (PPA) have distinct deficits in these domains (Budd et al., 2010; Sepelvak et al., 2011), Naming (word retrieval) and spelling can also be among the earliest functions impaired in MCI when language is the prominent affected domain. Currently there is no available proven treatment for these individuals. Transcranial Direct Current Stimulation (tDCS) is a relatively new, safe, non-invasive, non-painful electrical stimulation of the brain that has resulted in improved language and cognitive abilities in stroke and dementia (AD) when administered during traditional behavioral (language) therapy (Baker et al., 2010; Boggio et al., 2009; Ferrucci et al., 2008; Floel et al., 2011; Monti et al., 2008; Schlaug et al., 2008). tDCS alters neuropeptide concentrations at the sites of stimulation, which is particularly important because individuals with PPA have a specific neuropeptide signature. It has been shown that anodal tDCS can enhance language and motor performance, visuo-motor learning, and recognition memory or working memory. We are not aware of any studies investigating whether tDCS can improve the language and cognitive abilities of people with PPA. In this research project we intend to cover this gap by investigating the behavioral and neuromodulatory effects of tDCS during spelling therapy in PPA participants over time. We hypothesize that anodal tDCS when administered in combination with spelling, naming, or working memory therapy will improve language performance of PPA and MCI participants at least in the short term more than behavioral therapy alone and that improvements may generalize to some other cognitive functions. Research on the effects of tDCS in sleep and exercise is growing, but the effects are not yet conclusive. In some studies, tDCS has been found to improve sleep in individuals with fibromyalgia, bipolar disorder, and post-polio when premotor or motor areas are stimulated (Acler et al., 2013; Minichino et al., 2014; Roizenblatt et al., 2007), but it was found to depend on the area stimulated, i.e., it decreased sleep efficiency when the dorsolateral pre-frontal cortex was stimulated (Roizenblatt et al., 2007). The use of tDCS is more controversial in studies of exercise; some studies have shown increased post-exercise oxygen uptake with tDCS (Montenegro et al., 2012), while another has found similar perceived exhaustion rates for tDCS and sham (Okano et al., 2015). However, there are other reports that show that behavioral effects of tDCS depend on the task it is coupled with.

In this research project we will investigate whether and how tDCS alters the neuropeptide signature in participants with PPA and MCI. We will use proton magnetic resonance spectroscopy (H-MRS) to monitor

neuropeptide concentrations at the areas of stimulation. We hypothesize that tDCS will stabilize the decline a specific neuropeptide, but only in those areas of the brain where tDCS effectively resulted in more efficient gains in language compared to language therapy alone (with sham tDCS). Additionally, we will investigate whether brain-derived neurotrophic factor (BDNF) (i.e., the most common molecule associated with cognitive decline and impaired synaptic transmission in aging and neurodegeneration) is a sex-differentiated molecular determinant and mechanism of language and cognitive decline and treatment in neurodegeneration.

Study results may help optimize future intervention in individuals with PPA and MCI by providing treatment alternatives in a neurodegenerative condition with no proven effective treatment. A better understanding of the therapeutic and neuromodulatory effects of tDCS in PPA and MCI will offer insight into ways of impeding neurodegeneration that may improve quality of life for individuals with PPA and MCI and may provide insights into the mechanisms of this treatment for augmenting therapy for stroke as well.

## Objectives

**Primary Objective 1 (intervention):** To determine whether behavioral therapy coupled with anodal tDCS will improve the language performance of participants with PPA and MCI more efficiently and for greater duration than behavioral therapy alone (i.e. in the sham condition). tDCS targets will be the supramarginal gyrus (SMG), middle temporal gyrus (MTG) and inferior frontal gyrus (IFG). These areas are critical for both phoneme-grapheme conversion and for access to orthographic representation of words and their meaning in the spelling process (Cloutman et al., 2009). For individuals with naming or working memory/repetition deficits, tDCS targets will also be IFG, MTG, angular gyrus (AG), and SMG, as these are also areas of the brain consistently activated in these tasks (Jarso et al., 2013; Philipose et al., 2007). For individuals with executive functioning deficits, the tDCS target will be the dorsolateral prefrontal cortex (DLPFC) to compare language vs. executive functions after stimulation of the DLPFC. For individuals receiving home-based tDCS and computerized cognitive therapy, tDCS targets will include perisylvian areas and their right hemisphere homologs. For individuals receiving home-based tDCS there will be an optional 3-week cognitive behavioral therapy (CBT) where the tDCS target will be the LDLPFC.

Hypothesis 1a: Both behavioral therapy and combined tDCS-behavioral therapy will result in improved language performance for trained and untrained stimuli, from baseline to post-treatment; however, goals will be achieved more rapidly with the combined intervention.

Hypothesis 1b: Improvements in language achieved with combined tDCS-behavioral therapy but not behavioral therapy alone will persist at 2 weeks, 2 months and 6 months post-intervention. Hypothesis 1c: Stimulation of the propose areas during behavioral therapy will improve performance in other language and cognitive functions specific to the region of interest. Specifically, for SMG, improvements will be observed in spelling, naming, working memory and repetition; and for IFG and MTG, in spelling, naming, working memory, articulation, and syntactic comprehension. Hypothesis 1d: The therapeutic effect of tDCS will exhibit an interaction between hemisphere of stimulation (left vs. right) and stage of disease (early vs. middle), such that left hemisphere stimulation will be more effective at an early stage, whereas at later stages right hemisphere stimulation. Hypothesis 1e. Improvements in language achieved with combined IFG tDCS-behavioral therapy or sham and behavioral therapy alone will correlate with increases in daily physical activity and evening sleep efficiency and quality (using both self-report and objective measures) and there will be greater improvements in sleep efficiency and exercise in the tDCS condition as opposed to sham, because the area we target (left or right IFG) with 2x2 in electrodes incorporates premotor and motor areas that have

been found to improve the perceived difficulty and amount of exercise and sleep efficiency.

Hypothesis 1f: Beginning with a 3-week CBT treatment with tDCS over the DLPFC before beginning computerized cognitive/speech therapy at home will foster motivation and engagement in the consequent therapy by establishing routine, form, and helping manage psychological barriers to therapy beforehand.

**Primary Objective 2 (imaging):** To develop biomarkers for the effects of intervention using H-MRS. We will use H-MRS to detect NAA and GABA before, after and at follow-up intervals and evaluate the correlation between: (1) NAA/ GABA levels and (2) spelling, naming, and/or repetition accuracy of participants with PPA and MCI at each time point.

Hypothesis 2a: We hypothesize that tDCS coupled with behavioral therapy will result in enhanced, relative to behavioral therapy alone (with sham tDCS), levels of NAA at the stimulation sites where tDCS resulted in improved spelling relative to behavioral therapy alone.

Hypothesis 2b: We hypothesize that tDCS coupled with spelling therapy will result in reduced, relative to behavioral therapy alone (with sham tDCS), levels of GABA at the stimulation sites where tDCS resulted in improved language relative to behavioral therapy alone.

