#### Spelling

#### Treatment of the PGC mechanism (PGC intervention)

For the PGC intervention, patients will receive language therapy of either phoneme-grapheme correspondence (PGC) or study of particular words (lexical therapy) or other similar type of therapy depending on the particular spelling deficit of each patient. Up to 30 English sounds will be selected representing most common word-initial English phonemes (speech sounds). Then a set of up to 30 English words starting with these sounds will be used as prompts to help the participants relate each sound to a grapheme (abstract letter identity or sequence of letter identities). In the case of spelling therapy with words, sets of up to 50 English words with matched psycholinguistic characteristics (frequency, length etc) will be chosen and divided in sets for either baseline testing, training, homework, or repetition. In the case of PGC therapy, the participant will be either asked to provide the letters that would correspond to each sound and if failed to do so will be provided with word prompts. In the case of lexical therapy, the participant will be asked to spell the chosen words and if failed to do so will be taught the spelling of each word in the training set or proceed to the rest of the set in other sets. Words or PGCs will be taught in blocks of 10; when the patient reaches criterion (80% correct) he or she will continue to the other blocks. Individuals who reach criterion quickly will move to a second stage, in which they will be asked to write words beginning with each target phoneme. They will be assisted in correcting the spelling of the words by "sounding out" the word. Baseline evaluation before each therapy session will be held before each therapy session and will either require that the participant would choose--from a series of possible initial letters or letter sequences of English written in front of him or her--the letter or letter sequence that corresponds to the phoneme the examiner provides each time. Treatment of the lexical access mechanism (lexical access intervention).

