For the lexical access treatment we will follow the methodology of the only other published spelling intervention in PPA (Rapp & Glucroft, 2009). Stimuli will consist of three word sets (n=10 for each set) that will be matched for lexical frequency, letter length, regularity, and concreteness. We will use 10 stimuli for each set to better match the PGC and lexical treatments. Set 1 will serve as trained items for the first condition (either sham or tDCS), and set 2 as untrained items and then set 2 will serve as trained items JHMIRB eFormA 01

and set 3 as untrained. A spell-study-spell procedure (Beeson et al., 2013; Rapp & Glucroft, 2009) similar to that used in a number of other studies will be applied to the trained words, such that at every training session the patient will be asked: (1) to spell each word to dictation, (2) to study the word presented on a written note card and orally name each of its letters while the experimenter repeats the word, and (3) if the word has been spelled incorrectly to attempt to spell it again. This procedure will be repeated until the words of each set are correctly spelled for two consecutive sessions. If a word is spelled correctly on the first attempt, the word will still be presented for the participant to study and only then will the experimenter continue to the next word. Untrained words will be presented for spelling to dictation only at the time of the pre- and post-treatment evaluations and at two follow-ups to evaluate whether therapy gains generalize to the spelling of other words.

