#### 6. Study Statistics

#### *a. Primary outcome variable.*

The primary outcome measures will be: a) change in performance from pre- to post-treatment levels on the trained items (e.g. change in % accuracy in phoneme-grapheme conversion of trained phonemes, % accuracy naming of trained pictures, average % correct names produced in trained categories in 1 minute), and, b) generalization to untrained items, measured by change in performance from pre- to post-treatment levels on the trained items (e.g. change in % accuracy in phoneme-grapheme conversion of untrained phonemes, % accuracy naming of untrained pictures, average % correct names produced in untrained categories in 1 minute). For those individuals with DLPFC stimulation for executive functions, we will use an additional automated score from BrainHQ program training (Smith et al., 2009). For individuals

receiving home-based tDCS over the left perisylvian areas and their right hemisphere homologs, we will assess pre- to post- language scores.

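### Hypothesis 1a predicts faster gains with tDCS, but no outcome measures speed, and pre-to-post change on trained items can miss it when participants reach criterion within the block

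*Combined protocol and SAP*

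**What the plan says.** Under Objectives, Primary Objective 1 asks whether language improves "more efficiently and for greater duration than behavioral therapy alone". Hypothesis 1a then expects improvement in both conditions and states that "goals will be achieved more rapidly with the combined intervention".

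Section 6a defines the first primary outcome as "change in performance from pre- to post-treatment levels on the trained items". The second is the corresponding change for untrained items. Section 6b covers generalization to other functions. Section 6c analyses changes from before treatment to three times: immediately after, 2 weeks and 2 months. Nothing observed during a block enters any of these.

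Section 3a sets progression rules for the therapies:
- PGC and word blocks of 10: "when the patient reaches criterion (80% correct) he or she will continue to the other blocks". PGC has up to 30 sounds, and "Individuals who reach criterion quickly will move to a second stage".
- Lexical spelling, sets of 10 words: "This procedure will be repeated until the words of each set are correctly spelled for two consecutive sessions".
- Naming: the next level is reached at 100% on all trained sets.
- Repetition and BrainHQ training: no comparable mastery rule.

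For PGC the same section provides a measurement within the block: "Baseline evaluation before each therapy session will be held before each therapy session". For the lexical sets, "Untrained words will be presented for spelling to dictation only at the time of the pre- and post-treatment evaluations" and at follow-up. A condition lasts 5 to 15 sessions (tDCS methods); Table 1 shows 15.

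**The concern.** If both conditions improve and tDCS differs by getting there sooner, the informative data lie inside the block. A comparison made only after the block sees a difference in speed through what remains of it at the end. Training to a mastery criterion shrinks that remainder, because once both conditions are near the top of the trained set there is little left to separate them.

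At stake is the reading of a null result. tDCS could act as Hypothesis 1a says and the trained-item change could still show almost nothing. The trial would then have no prespecified analysis to tell no difference in speed from a difference that was not measured.

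**Working it through.** **1. The plan's own power figure.** Section 6c gives 30 participants, design effect 1.5, effect size 0.8 and power 75%. Alpha and sidedness are not stated; two-sided 5% is assumed. With 15 per arm × 1.5 = 22.5 per arm:

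0.8 × √(22.5/2) = 2.683; 2.683 − 1.960 = 0.723; Φ(0.723) = 76.5%. The noncentral t gives 74.6%.

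The 75% is reproduced. It refers to a pre-to-post change and says nothing about speed.

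**2. Hypothesis against measurement.**

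| Element of 1a | Matching outcome or analysis |
|---|---|
| Trained items improve | 6a, first outcome |
| Untrained items improve | 6a, second outcome |
| tDCS reaches the goals sooner | none in 6a, 6b or 6c |

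**3. When end accuracy loses the signal.** Assume an item is learned in a session with probability 1 − exp(−r), with r = ln 2/m under sham (m = median sessions to learn an item) and 1.5r under tDCS. Ignoring variation between people, the gap in end accuracy after S sessions is 2^(−S/m) − 2^(−1.5S/m):
- S = 15, m = 2: 0.0055 − 0.0004 = 0.5 points
- S = 15, m = 5: 0.1250 − 0.0442 = 8.1 points
- S = 5, m = 3: 0.3150 − 0.1768 = 13.8 points

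**4. Power in the same model.** 30 participants in a paired crossover, 10 items, SD of the log rate 0.5 between and 0.3 within participants, paired t test at two-sided 5%. Criterion is the full set correct in two consecutive sessions, censored at block end. The rates, the 1.5 ratio and the SDs are assumptions.

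| Sessions | m | End accuracy, sham v tDCS | Power: end accuracy | Power: sessions to criterion | Power: mean session accuracy |
|---|---|---|---|---|---|
| 15 | 1 | 99.6 v 99.9% | 1% | 75% | 84% |
| 15 | 2 | 97.2 v 99.1% | 25% | 79% | 89% |
| 15 | 3 | 93.1 v 97.2% | 51% | 76% | 90% |
| 15 | 5 | 83.7 v 91.6% | 71% | 63% | 88% |
| 15 | 8 | 71.0 v 82.1% | 80% | 41% | 87% |
| 5 | 1 | 93.2 v 97.2% | 49% | 74% | 85% |
| 5 | 3 | 67.4 v 79.3% | 81% | 27% | 89% |
| 5 | 8 | 37.6 v 49.3% | 73% | 0% | 72% |

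The last column comes from a separate run, so differences of 2 or 3 points between columns are simulation error. At 15 sessions, 96%, 79%, 60%, 32% and 13% of sham participants reach criterion as m goes from 1 to 8. End accuracy weakens as that share rises.

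**5. A second model.** Fixed chance per session, SDs 0.5 (person) and 0.3 (condition) on the logit scale:
- 0.20 v 0.26, 10 words, 15 sessions: power 38% (end change), 63% (sessions to 80%), 73% (mean accuracy).
- Same rates, 5 sessions: end accuracy 66% v 75%; power 59% (end change) v 49% (sessions to 80%).
- 0.05 v 0.07, 15 sessions: 68% v 42%, same order.
- 30 PGC items in three blocks of 10, moving on at 80%, all 30 scored, 15 sessions, tested at 0.15 v 0.20, 0.20 v 0.26 and 0.25 v 0.32: end change 73% to 83%, sessions to first-block criterion 62% to 64%.

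**6. Session-start scoring.** The mean accuracy above counts items after each session. An attempt at the start of session s reflects s − 1 sessions, so its average lags by one. A recheck of the model in step 4 gave the same power at 15 sessions to within simulation error. With 5 sessions and m = 8 it fell below end accuracy (67% v 74%).

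**The case against.** A reader might infer that training to criterion hides any difference in speed, and that the trained-item primary outcome should therefore be replaced. The documents do not support that.

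- Blocks are capped at 5 to 15 sessions. With a fixed number of sessions, faster learning raises end accuracy unless participants reach the ceiling, and the documents do not say how many will.
- In PGC, reaching 80% leads to new sounds, up to 30, so a faster learner covers more and scores higher. This is the task that section 6c names for the behavioural analysis.
- Untrained items are a primary outcome and are not trained to criterion.
- The tDCS methods section states the expected benefit over sham in terms of pre-to-post accuracy, so the main efficacy claim and the outcome do match.

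All of this stands and limits where the problem bites. None of it supplies a measure of speed.

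A reader might also infer that sessions to criterion is the natural replacement. Steps 4 and 5 show that it loses to end accuracy when blocks are short, learning is slow or the item pool is large. The criteria also differ between therapies, so pooling would need further definitions.

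Lastly, it would be too strong to say that the data are already recorded. Section 3a describes a per-session evaluation for PGC. For lexical spelling and naming it describes a first attempt at each word or picture, but no scored record.

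**Conclusion.** The speed clause of Hypothesis 1a cannot be tested with the outcomes and analyses as written; this follows from the text alone. It is a separate and conditional point that pre-to-post change on trained items can miss a difference in speed. That happens when participants reach criterion within the block, chiefly in the 10-word lexical sets and in naming trained to 100%. It is less of a problem for PGC with up to 30 sounds, for short blocks and for slow learners, and it does not apply to untrained items.

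Under the assumed 1.5-fold rate, the power of end accuracy runs from about 1% to 80% at 15 sessions, depending on learning speed. Mean session accuracy stays at 84% to 90%. It matched or beat end accuracy to within simulation error in every scenario when scored after each session. Start-of-session scoring costs a few points in the shortest blocks with slow learners. The models omit forgetting and rest on assumed rates, so the sizes are illustrative. They justify adding a measure of speed but not discarding the present primary outcome.

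**What to change.** Keep pre-to-post change as the primary outcome for trained and untrained items. In section 6, add as the prespecified test of Hypothesis 1a's speed clause: mean accuracy on trained items over the session-start attempts within each block, averaged over the sessions given, compared between tDCS and sham with the same within-patient permutation test. Say which sessions enter if a participant's two blocks differ in length. List sessions to criterion, censored at block end and with the criterion defined for each therapy, as supportive only.

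In section 3a, state that the first uncued attempt at each session is scored and recorded in every therapy to which this test applies.

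The cost is one more prespecified analysis and a little scoring work. The therapy and the stated power need not change, because the primary outcome stays as it is.
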